In view of the COVID-19 pandemic, alternative arrangements to conduct study visits according to the protocol may be considered.

- ^a Screening and signing of the informed consent form (ICF) will occur at baseline (Day 1), which is also the day of Dose 1 vaccination. If needed, the screening activities may be split over multiple visits, with a maximum time of up to 28 days between signing the ICF and Dose 1 vaccination.
- ^b In addition to the assessments scheduled during the study site visits, participants will be instructed to contact the investigator before the next visit if they experience any adverse event or intercurrent illness that they perceive as relevant and/or can be possibly related to study vaccine in their opinion.
- ^c Signing of the ICF needs to be done before the first study-related activity.
- ^d The investigator should ensure that all study enrollment criteria have been met at the end of screening. If a participant's clinical status changes (including receipt of additional medical records) after screening but before Dose 1 vaccination such that he/she no longer meets all eligibility criteria, then the participant should be excluded from further participation in the study.

- ^e Prestudy-specific therapies such as analgesic/antipyretic medications, nonsteroidal anti-inflammatory drugs, vaccines, and immunomodulators/suppressors (eg, cancer chemotherapeutic agents, systemic corticosteroids) administered up to 30 days prior to Dose 1 vaccination and previous vaccinia/smallpox vaccination at any time prior to study entry must be recorded in the electronic case report form (eCRF).
- ^f The investigator must check for acute illness or body temperature $\geq 38.0^{\circ}\text{C}$ at the time of vaccination. In such cases, the participant may be vaccinated up to, and no later than 10 days after the scheduled vaccination, or be withdrawn at the discretion of the investigator and after consultation with the sponsor.
- ^g Prior to study vaccine administration.
- ^h For women of childbearing potential.
- ⁱ A full physical examination (excluding genito-urinary system), including height and body weight, will be carried out at screening (Day 1). At other visits, an abbreviated, symptom-directed examination will be performed as indicated by the investigator.
- ^j Includes blood pressure and pulse/heart rate (at least 5 minutes of rest in supine position), and oral temperature.

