- ^q Concomitant therapies such as analgesic/antipyretic medications, nonsteroidal anti-inflammatory drugs, vaccines, and immunomodulators/suppressors (eg, cancer chemotherapeutic agents, systemic corticosteroids) must be recorded from Dose 1 vaccination up to 28 days post Dose 1 vaccination and from Dose 2 vaccination up to 28 days post Dose 2 vaccination. All other concomitant therapies should also be recorded beyond these time frames until the end of the study (ie, 6 months post Dose 2) if administered in conjunction with serious adverse events and pregnancies (if applicable).
- ^r This is not required for participants in Groups 5-6 (Booster Cohort).
- ^s Humoral immunogenicity assessments on Days 1, 57, and 78; determination of neutralizing antibodies against the Ad26 vector on Day 1 for Groups 5-6 (Booster Cohort) only.
- ^t Informed consent for Groups 5-6 (Booster Cohort) includes additional procedures. See below.
- ^u Lower limit: Day 57-3 days, upper limit: Day 57+28 days

Additional Visits for Groups 5-6	Booster	Vaccination and Postvaccination Visits ^a				Follow-up	
	Day 177 ±1w	Day 184 ±2d	Day 198 ±3d	Day 205 (Telephone call for safety follow-up) ±1w	Day 357 ±2w	Day 537 ±4w	
Study Procedures	Booster Dose 4 months post Dose 2	7 days post booster dose	21 days post booster dose	28 days post booster dose	6 months post booster dose	12 months post booster dose	
Screening/Administrative							
Prevaccination symptoms ^b	X						
Study vaccine administration	▲						
Immunogenicity Assessments							
Blood sampling for immunogenicity assays (8.5 mL per blood draw) ^c	X ^d	X	X		X	X	
Safety Assessments							
Urine pregnancy test ^e	X ^d						
Physical examination ^f	X ^d	X ^f	X ^f				
Vital signs ^g	X ^d	X ^g	X ^g				
Distribution of participant diary ^h	X						
Review of participant diary by study site personnel ⁱ		X					
30-minute postvaccination observation ^j	X						
Solicited adverse events recording ^k	From booster vaccination until 7 days post booster						
Unsolicited adverse events recording ^{l,m}	From booster vaccination until 28 days post booster						
Pregnancy, serious adverse events ^l	Continuous						
Concomitant medications ⁿ	From booster vaccination until 28 days post booster				X ⁿ		

▲ Ad26.ZEBOV 5x10¹⁰ vp

d: days; w: week

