^a In addition to the assessments scheduled during the study site visits, participants will be instructed to contact the investigator before the next visit if they experience any adverse event or intercurrent illness that they perceive as relevant and/or can be possibly related to study vaccine in their opinion.

^b The investigator must check for acute illness or body temperature $\geq 38.0^{\circ}\text{C}$ at the time of vaccination. In such cases, the participant may be vaccinated up to, and no later than 10 days after the scheduled vaccination or be withdrawn at the discretion of the investigator and after consultation with the sponsor.

^c Humoral immunogenicity assessments on Days 177, 184, 198, 357 and 537; assessment of neutralizing antibodies against the Ad26 vector on Days 177 and 198.

^d Prior to study vaccine administration.

^e For women of childbearing potential.

- f An abbreviated, symptom-directed examination will be performed as indicated by the investigator.
- g Includes blood pressure and pulse/heart rate (at least 5 minutes of rest in supine position), and oral temperature.
- h Participants will receive a diary to document symptoms of solicited local and systemic adverse events (reactogenicity).
- i The participants will complete diary cards until 7 days post each vaccination (solicited adverse events), which will be reviewed by study site personnel at the Day 184 visit.
- j After each vaccination, participants will remain under observation at the study site for at least 30 minutes for presence of any acute reactions or solicited events. Solicited and unsolicited adverse events emerging during the observation period will be recorded in the eCRF.
- k Solicited adverse events will be documented in the evening after each vaccination and then daily for the next 7 days.
- l All adverse events and special reporting situations, whether serious or nonserious, that are related to study-related procedures or to non-investigational (concomitant) sponsor products, and pregnancy (if applicable), will be reported from the time a signed and dated ICF is obtained onwards. Other serious adverse events and special reporting situations will be reported from first dose of study vaccine until the end of the study. Other nonserious adverse events and special reporting situations will be reported from first dose of study vaccine until 28 days after booster dose of study vaccine.

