 - If acute illness (excluding minor illnesses such as diarrhea or mild upper respiratory tract infection) or fever (body temperature $\geq 38.0^{\circ}\text{C}$) occur at the scheduled time for vaccination, the participant may be vaccinated up to 10 days beyond the window allowed for the scheduled vaccination, or be withdrawn from that vaccination at the discretion of the investigator and after consultation with the sponsor (see Section 6.1).
 - Contraindications to Dose 2 and booster dose vaccination are included in Section 6.2.

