Due to the recent (on 11 March 2020) WHO declared COVID-19 pandemic, a potential higher dropout rate (ie, higher than 5%) may occur. In addition, some participants in the immunogenicity subset may be excluded from primary immunogenicity equivalence testing because of:

- Participant not receiving Dose 2; *OR*
- Participant receiving Dose 2 outside the protocol-defined window; *OR*
- Participant not attending the 21-day post Dose 2 visit; *OR*

- Participant attending the 21-day post Dose 2 visit outside the protocol-defined window.

To mitigate these issues, additional participants may be recruited in the immunogenicity subset.

Shortly after participants received Dose 1 vaccination, ‘stay-at-home’ orders were imposed in the areas where the sites were located. Although the sites had implemented appropriate safety measures to prevent spread of SARS-CoV-2, approximately 22% of participants did not return to the site within the protocol defined windows (± 3 days) for Dose 2 administration. Investigators were instructed to bring participants back to the site to complete the vaccine regimen, even if they were out of window. Currently, the stay-at-home orders have been lifted and participants are now able to return to the sites for follow-up. In order to reduce the number of additional participants needed for the primary and secondary immunogenicity analyses, it is possible to widen the acceptable window around Dose 2 administration without jeopardizing the primary and secondary objectives of the study. The protocol has been amended to widen the upper limit of the window around Day 57 (Dose 2) to Day 85 (ie, Day 57+28 days). Therefore, the number of additional participants necessary for inclusion in the immunogenicity subset and who would receive their second vaccination within the Day 57 window will be reduced.

For the Booster Cohort (Groups 5-6), a planned total of 60 participants will be enrolled. All participants in this cohort will be assessed for safety, reactogenicity, and immunogenicity. Participants will be randomly assigned to the 2 groups in a 5:1 ratio, ie, to a group of approximately 50 participants receiving the primary vaccine regimen (Ad26.ZEBOV followed by MVA-BN-Filo 56 days later) followed by a booster dose of Ad26.ZEBOV 4 months after Dose 2 (Group 5), or, to a placebo group of approximately 10 participants (Group 6).

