6. DOSAGE AND ADMINISTRATION

An overview of the study vaccination schedule is provided in Section 3.1, Table 1. All participants will receive a vaccination, according to randomization, on Day 1, on Day 57, and on Day 177 (Groups 5-6 only) at the following dose levels:

- Ad26.ZEBOV: 5×10^{10} vp, supplied in a single-use vial (0.5 mL extractable) (Groups 1, 2, 3, 5);
- MVA-BN-Filo: 1×10^8 Inf U, supplied in a single-use vial (0.5 mL extractable) (Groups 1, 2, 3, 5);
- Placebo: 0.9% saline, 0.5 mL (Groups 4 and 6).

Blinding will be achieved by preparation of study vaccine by unblinded qualified study site personnel not involved in any other study-related procedure, and by the administration of study vaccine in a masked syringe by a blinded study vaccine administrator.

Ad26.ZEBOV and MVA-BN-Filo, or placebo, will be administered as 0.5-mL IM injections in the deltoid muscle. The injection site should be free from any injury, local skin condition, or other issue that might interfere with the evaluation of local reactions (eg, significant tattoo). In each participant, it is recommended that the second vaccination is administered in the opposite deltoid muscle from the first vaccination (unless the opposite arm has a condition that prevents evaluating the arm after injection) and it should be recorded in the eCRF in which arm the vaccination has been administered. The booster dose may be administered in either deltoid. No local or topical anesthetic will be used prior to the injection.

After each vaccination, participants will remain at the study site for at least 30 minutes for presence of any acute reactions and solicited events, or longer if deemed necessary by the investigator (eg, in case of grade 3 adverse events).

As with any vaccine, allergic reactions following vaccination with the study vaccine are possible. Therefore, appropriate drugs and medical equipment to treat acute anaphylactic reactions must be immediately available and a medically qualified member of the study site personnel trained to recognize and treat anaphylaxis must be present at the study site during the entire vaccination procedure and postvaccination monitoring period.

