6.1. Criteria for Postponement of Vaccination

A participant will not be given any study vaccine if he or she experiences any of the following events at the scheduled time for vaccination:

- Acute illness at the time of vaccination (this does not include minor illnesses such as diarrhea or mild upper respiratory tract infection);
- Fever (body temperature $\geq 38.0^{\circ}\text{C}$) at the time of vaccination.

Participants experiencing any of the events described above may be vaccinated up to 10 days beyond the window allowed for the scheduled vaccination, or be withdrawn from that vaccination at the discretion of the investigator and after consultation with the sponsor.

Note: In case Dose 2 or booster dose vaccination is postponed, the timing of the post Dose 2 or post booster dose visits will be planned relative to the actual vaccination day.

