- Participant not receiving Dose 2; *OR*
- Participant receiving Dose 2 outside the protocol defined window; *OR*
- Participant not attending the 21-day post Dose 2 visit; *OR*
- Participant attending the 21-day post Dose 2 visit outside the protocol-defined window.

To mitigate these issues, additional participants may be recruited in the immunogenicity subset.

Shortly after participants received Dose 1 vaccination, ‘stay-at-home’ orders were imposed in the areas where the sites were located and approximately 22% of participants did not return to the site within the protocol defined windows (± 3 days) for Dose 2 administration.

Examination of the immunogenicity data from studies (VAC52150EBL2001 and VAC52150EBL2002) in which Dose 2 was administered at intervals ≥ 56 days reveals that although there appears to be trend of increasing GMCs with increasing intervals between Dose 1 and Dose 2, the variability (standard deviation) of the immune responses (binding antibody levels against the EBOV GP using ELISA [EU/mL]) remains stable and in line with the currently assumed standard deviation of 0.55 (on the \log_{10} -scale). Assuming that the delayed Dose 2 administration will be randomly distributed among the groups (ie, Groups 1-4), widening the acceptable time frame to administer Dose 2 by increasing the upper limit of the window to 28 days (ie, Day 57+28 days) is not expected to adversely affect the primary and secondary objectives of the study. With the widened window, the number of additional participants necessary to maintain approximately 90% power to test the primary and secondary hypotheses will be reduced.

Approximately 60 participants will be randomized in a 5:1 active:placebo ratio (Group 5:Group 6), which will provide a reasonable estimation of the humoral immune response to a booster dose.

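### Schedule footnotes f and b cap an illness-postponed dose at 10 days after the scheduled vaccination, while Sections 1.2.5 and 6.1 allow 10 days beyond the window; since Amendment 3 the cap can fall inside the Groups 1-4 Dose 2 window (minor)

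*Protocol*

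**What the plan says.** Four places in the protocol set a limit for vaccinating someone who is acutely ill or has a temperature of at least 38.0°C when the dose is due.

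- Time and Events Schedule, footnote f (Dose 1 and Dose 2): "the participant may be vaccinated up to, and no later than 10 days after the scheduled vaccination".
- Time and Events Schedule for Groups 5-6, footnote b (booster): the same limit, "no later than 10 days after the scheduled vaccination".
- Section 1.2.5: "the participant may be vaccinated up to 10 days beyond the window allowed for the scheduled vaccination".
- Section 6.1, the section on postponement: "may be vaccinated up to 10 days beyond the window allowed for the scheduled vaccination".

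The first two count from the scheduled vaccination, the last two from the end of the window. Section 6 places Dose 2 on Day 57. Footnote u gives the Groups 1-4 window as "Lower limit: Day 57-3 days, upper limit: Day 57+28 days", that is, Days 54 to 85. For Groups 5-6 the Schedule allows ±1 week at Dose 2 and at the booster.

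Protocol 11.1 and SAP 2.3.2 require Dose 2 within the protocol-defined window for the per protocol set. SAP 1.2 ties that term to the Amendment 3 visit windows. No passage says whether the footnotes or Section 6.1 takes precedence.

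**The concern.** Section 9.1.1 sends sites to the Schedule for timing and visit windows, so a footnote there works as a dosing rule. A site that follows footnote f could turn away a participant who has recovered, on a day when Section 6.1 allows the dose and the per protocol timing rule accepts it. That would work against Section 3.1, which explains the wider window as a way to reduce the number of additional participants needed.

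Footnote f also speaks of the participant being withdrawn without saying from what. Section 6.1 limits withdrawal to that vaccination, and Section 10.2 says that stopping vaccine does not by itself end study participation. At stake are a few avoidable missed second doses, and the same number of avoidable losses from the per protocol set if those participants are in the immunogenicity subset.

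**Working it through.** **1. The plan's own figures.** The window is 57 − 3 = Day 54 to 57 + 28 = Day 85, as stated. For sample size, 0.90^(1/3) = 0.9655, the stated 96.55% per pair. With SD 0.55 (log10), true ratio 0.9, limits 0.5 and 2.0 and a 95% CI (Protocol 11.2 and 11.3), a normal approximation needs 133 evaluable per group, or 133 / 0.95 = 140 enrolled, against 144 planned. At 144 × 0.95 = 136.8, about 137 evaluable, pairwise power by noncentral t is 96.85%.

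**2. Limits, taking the scheduled day as the nominal day.**

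| Dose | Window end | Footnote limit | Section 6.1 limit | Gap (days) |
|---|---|---|---|---|
| Dose 2, original ±3 days | 60 | 57+10 = 67 | 57+3+10 = 70 | 3 |
| Dose 2, Groups 1-4, Amendment 3 | 85 | 57+10 = 67 | 57+28+10 = 95 | 28 |
| Dose 2, Groups 5-6 | 64 | 57+10 = 67 | 57+7+10 = 74 | 7 |
| Booster, Groups 5-6 | 184 | 177+10 = 187 | 177+7+10 = 194 | 7 |

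Only in the second row does the footnote limit come before the window end. The window there has 85 − 54 + 1 = 32 days. Days 68 to 85 are 85 − 68 + 1 = 18 of them.

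**3. Limits, taking the scheduled day as the booked day d.** In-window days barred = max(0, 85 − (d + 10)) = max(0, 75 − d). This is 21 for d = 54, 18 for d = 57, 1 for d = 74, and 0 from d = 75. Under the original window the earliest booking, Day 54, gave Day 64, after the Day 60 window end, so nothing was barred on this reading either. In Groups 5-6 at Dose 2 it is max(0, 64 − (d + 10)) = max(0, 54 − d): 4 for d = 50, 1 for d = 53, and 0 from d = 54.

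**4. People affected (assumptions, not document figures).** The documents give no illness rate at Dose 2, no recovery times and no distribution of Dose 2 days after Day 60. They say only that "approximately 22% of participants did not return to the site within the protocol defined windows". Take people = 741 × (share ill or febrile at Dose 2) × (share of those who would be dosed after Day 67). I assume 0.5% to 5% for the first share and 5% to 22% for the second.

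- Low end: 741 × 0.005 × 0.05 = 0.19.
- 1% ill: 741 × 0.01 × 0.05 = 0.37, to 741 × 0.01 × 0.22 = 1.63.
- 2% ill: 0.74 to 3.26.
- High end: 741 × 0.05 × 0.22 = 8.15.

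The base of 741 includes placebo and safety-only participants, and anyone already given Dose 2 when Amendment 3 took effect.

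**5. Effect on the primary test.** Suppose all 8 were active immunogenicity-subset participants spread evenly over three groups, about 3 per group (8 / 3 = 2.7). Pairwise power then goes from 96.85% (n = 137) to 96.53% (n = 134). Losing 2 per group gives 96.64% and losing 5 gives 96.30%.

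**6. Days 86-95.** Section 6.1 permits a postponed Groups 1-4 dose until Day 95, but the per protocol window closes on Day 85. A dose on those 10 days completes the regimen and does not qualify for the per protocol set.

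**The case against.** The strongest case against has three parts.

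First, the people most likely to be dosed late had to be rebooked, and for them the scheduled vaccination naturally means the new appointment. A booking from Day 75 on then loses nothing, and an earlier booking loses a dose only if the illness lasts beyond 10 days. This narrows the problem but does not remove it: bookings on Days 54-74 still have a limit inside the window.

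Second, Section 6.1 is the dedicated section, Section 1.2.5 repeats its rule and refers to it, and Section 10.2 points back to it. Footnote f requires consultation with the sponsor, and Section 3.1 records that investigators were told to complete the regimen even out of window. All of this stands and makes an actual refusal unlikely. It does not correct the text: in footnote f the consultation goes with withdrawal, not with the day limit.

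Third, the mismatch is older than Amendment 3, at 3 days. That is correct. Amendment 3 raised the gap to 28 days on the nominal-day reading and made it reach in-window days.

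A reader might infer that footnote f closes Days 68-85 to Groups 1-4 in general. It does not. It applies only to someone ill or febrile when the dose is due.

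**Conclusion.** The inconsistency is real and minor, and footnote f is wrong as written for Groups 1-4. It can bar in-window, per-protocol-eligible second doses for ill or febrile participants: up to 18 of 32 days on the nominal-day reading, and 1 to 21 days for bookings on Days 54-74 on the other.

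A reader might want to take a headcount from the 22% figure. The documents do not support one. That figure counts people who missed ±3 days for any reason, not people who were ill, and the number still undosed at Amendment 3 is not given. The range of about 0.2 to 8 rests wholly on the assumed shares. Nor do the documents support reading this as a threat to the equivalence test: the power change is a fraction of a percentage point, and the type I error rate is untouched.

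In Groups 5-6 the two rules differ only outside the window on the nominal-day reading. On the booked-day reading the Dose 2 limit enters the window only for bookings on Days 50-53. Alignment there is a consistency edit.

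**What to change.** Replace the day limit in footnotes f and b with the Section 6.1 rule, "may be vaccinated up to 10 days beyond the window allowed for the scheduled vaccination", and limit the withdrawal option to that vaccination, as Section 6.1 does. All four places then agree.

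Add one sentence for Groups 1-4: a dose on Days 86-95 is permitted to complete the regimen but is outside the −3/+28-day window, so it is excluded from the per protocol set.

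For Groups 5-6, the sponsor should confirm that a Dose 2 as late as Day 74 is acceptable, given the concern in Section 3.1 about shortening the interval to the booster. With the booster on Day 177 that interval would be 177 − 74 = 103 days instead of 177 − 57 = 120. If the re-timing rule in Section 9.1.1 covers the booster visit, the interval stays at 120 days, and the text should say so.

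The cost is two reworded footnotes and a sentence or two, in a site clarification letter or the next amendment. The SAP and sample size do not change. The correction was still useful at Amendment 3: Groups 5-6 had not been recruited, and "additional participants may be recruited in the immunogenicity subset".

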1. INTRODUCTION

Janssen Vaccines & Prevention B.V. (hereafter referred to as the sponsor), in collaboration with Bavarian Nordic GmbH (BN), is investigating the potential of a prophylactic Ebola vaccine regimen (VAC52150) comprised of the following 2 candidate Ebola vaccines:

Ad26.ZEBOV is a monovalent vaccine expressing the full-length glycoprotein (GP) of the Ebola virus (EBOV, formerly known as *Zaire ebolavirus*) Mayinga variant. The vaccine is produced in the human cell line PER.C6®.

MVA-mBN226B, further referred to as Modified Vaccinia Ankara (MVA)-BN®-Filo, is a multivalent vaccine expressing the EBOV Mayinga GP, the Sudan virus (SUDV) Gulu GP, the Marburg virus (MARV) Musoke GP, and the Tai Forest virus (TAFV, formerly known as *Côte d'Ivoire ebolavirus*) nucleoprotein (NP). The EBOV GP expressed by MVA-BN-Filo has 100% homology with the one expressed by Ad26.ZEBOV.

For the most comprehensive nonclinical and clinical information regarding Ad26.ZEBOV and MVA-BN-Filo, refer to the latest versions of the Investigator's Brochures (IB) and Addenda.^{3,4} A brief summary of the clinical information available at the time of the protocol writing is provided below.

The term "study vaccine" throughout the protocol, refers to study vaccine (Ad26.ZEBOV, MVA-BN-Filo), or placebo.

The term "sponsor" used throughout this document refers to the entities listed in the Contact Information page(s), which will be provided as a separate document.

